#### **Adverse Events**

Adverse events will be reported by the subject (or, when appropriate, by a caregiver, surrogate, or the subject's legally acceptable representative) for the duration of the study. Adverse events will be followed by the investigator as specified in Section 12, Adverse Event Reporting.

## **Clinical Laboratory Tests**

Blood samples for hematology and coagulation profile will be collected as per protocol. The investigator must review the laboratory results, document this review, and record any clinically relevant changes occurring during the study in the adverse event section of the CRF. The laboratory reports must be filed with the source documents.

The following tests will be performed by the local laboratory

Hematology Panel

-hemoglobin

-hematocrit

-red blood cell (RBC) count

-platelet count

[-percent reticulocytes]

-absolute lymphocyte count (ALC)

-coagulation (PT, INR and aPTT)

-white blood cell (WBC) count with differential

Note: A WBC evaluation may include any abnormal cells, which will then be reported by the laboratory. A RBC evaluation may include abnormalities in the RBC count, RBC parameters, or RBC morphology, which will then be reported by the laboratory. In addition, any other abnormal cells in a blood smear will also be reported.

## Physical examination and Vital Signs

Physical examination and vital sign parameters will be documented at the participating site. Physical examination and vital sign parameters will include blood pressure, pulse rate, respiratory rate, body temperature, and weight.

# 9.3. Sample Collection and Handling

The sponsor will provide reimbursement for specific investigations to be conducted as listed in TIME AND EVENTS SCHEDULE. The sample collection and handling procedures for these investigations, conducted if any, must be performed as per the guidelines prescribed by the local laboratory practice.

The actual date of sample collection must be recorded in the CRF or laboratory requisition form.

# 10. SUBJECT COMPLETION/DISCONTINUATION OF STUDY TREATMENT/ WITHDRAWAL FROM THE STUDY

#### 10.1. Completion

The study will be considered completed with the EOS within the study for the last patient participating in the study. A subject will be considered to have completed the study if he or she has completed the telephonic assessments at month 13.

Last completed assessment of subjects who prematurely discontinue study treatment for any reason before completion of this phase IV study will be considered for analysis.

The sponsor reserves the right to close a participating site for data collection or to terminate the study at any time for any reason at the sole discretion of the sponsor. A participating site is considered closed when all required documents and study specific supplies have been collected and a site closure assessment has been performed.

The participating physician may initiate site closure at any time, provided there is reasonable cause and sufficient notice is given in advance of the intended termination.

Reasons for the early closure of a participating site by the sponsor or participating physician may include but are not limited to:

- Failure of the participating physician to comply with the protocol, requirements of the IRB or local health authorities, or the sponsor's procedures, or GCP guidelines;
- Inadequate recruitment of subjects by the participating physician.

# 10.2. Discontinuation of Study Treatment/Withdrawal from the Study

# Withdrawal From the Study

A subject will be withdrawn from the study for any of the following reasons:

- Lost to follow-up
- Withdrawal of consent
- [Death]

If a subject discontinues study drug and withdraws from the study before the end of the study duration, [end-of-treatment] [and] [posttreatment] assessments should be obtained.

If a subject is lost to follow-up, every reasonable effort must be made by the study-site personnel to contact the subject and determine the reason for discontinuation/withdrawal. The measures taken to follow up must be documented.

When a subject withdraws before completing the study, the reason for withdrawal is to be documented in the CRF and in the source document. Subjects who withdraw will not be replaced. If a subject withdraws from the study before the end of the study duration, end-of-treatment and post treatment assessments should be obtained.

## 11. STATISTICAL METHODS

Statistical analysis will be done by the sponsor or under the authority of the sponsor. A general description of the statistical methods to be used to analyze the efficacy and safety data is outlined below. Specific details will be provided in the Statistical Analysis Plan.

# 11.1. Subject Information

For all subjects who receive at least 1 dose of study drug descriptive statistics will be provided.

# 11.2. Sample Size Determination

The primary objective of this study is to estimate the incidence of AEs in Indian subjects under actual conditions of use of ImbruvicaTM. A sample size of 75 subjects is as per the recommendations of Subject Expert Committee (Oncology & Haematology) made in its 70th meeting held on 23rd May 2018 at Central Drugs Standard Control Organization HQ, New Delhi communicated vide F.N. 12-10/2017-DC (Pt-Johnson-snd).

# 11.3. Efficacy Analyses

Statistical analyses will be performed by or under the authority of the sponsor. A general description of the planned statistical methods to be used to analyze the data collected in this study is presented in the following subsections. Additional details will be provided in the statistical analysis plan.

No formal hypothesis testing will be conducted for this study. Data will be summarized using descriptive statistics. Continuous variables will be summarized using descriptive statistics, which will include the number of subjects, mean, standard deviation, median, minimum, and maximum. Categorical variables will be summarized using frequencies and percentages, as appropriate. Exploratory endpoints will be summarized using descriptive statistics.

#### 11.4. Safety Analyses

# **Adverse Events**

The verbatim terms used in the CRF by investigators to identify adverse events will be coded using the Medical Dictionary for Regulatory Activities (MedDRA). Treatment-emergent adverse events are adverse events with onset during the treatment phase or that are a consequence of a pre-existing condition that has worsened since baseline. All reported adverse events will be included in the analysis. For each adverse event, the percentage of subjects who experience at least 1 occurrence of the given event will be summarized by treatment group.

Summaries, listings, datasets, or subject narratives may be provided, as appropriate, for those subjects who die, who discontinue treatment due to an adverse event, or who experience a severe or a serious adverse event.

#### **Clinical Laboratory Tests**

Laboratory data will be summarized by type of laboratory test. Reference ranges and markedly abnormal results (specified in the Statistical Analysis Plan) will be used in the summary of laboratory data. Descriptive statistics will be calculated for each laboratory analyte at baseline and for observed values and changes from baseline at each scheduled time point. Frequency tabulations of the changes from baseline. Changes from baseline results will be presented in pre- versus

posttreatment cross-tabulations (with classes for below, within, and above normal ranges). [Frequency tabulations of the abnormalities will be made. A listing of subjects with any laboratory results outside the reference ranges will be provided. A listing of subjects with any markedly abnormal laboratory results will also be provided.

Parameters with predefined National Cancer Institute Common Terminology Criteria for Adverse Events (NCI-CTCAE) toxicity grades will be summarized. Change from baseline to the worst adverse event grade experienced by the subject during the study will be provided as shift tables.

# **Vital Signs**

Descriptive statistics of temperature, pulse/heart rate, respiratory rate, and blood pressure (systolic and diastolic values) and changes from baseline will be summarized at each scheduled time point. The percentage of subjects with values beyond clinically important limits will be summarized.

Descriptive statistics will be calculated at baseline and for observed values and changes from baseline at each scheduled time point. Frequency tabulations of the abnormalities will be made.

# **Physical Examination**

Descriptive statistics of changes from baseline will be summarized at each scheduled time point.

Physical examination findings will be summarized at each scheduled time point. Descriptive statistics will be calculated at baseline and for observed values and changes from baseline at each scheduled time point. Frequency tabulations of the abnormalities will be made.

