## 9.2. Safety Evaluations

Any clinically relevant changes occurring during the study will be recorded in the Adverse Event section of the CRF. Any clinically significant abnormalities persisting at the end of the study or at discontinuation will be followed by the participating physician until resolution or until a clinically stable outcome is reached.

All non-haematological AEs including laboratory AEs and AEs leading to dose reductions or discontinuation will be graded and reported according to the National Cancer Institute Common Terminology Criteria for Adverse Events (NCI-CTCAE), Version 4.0. All haematological AEs will be graded and reported according to the IWCLL 2008 criteria for grading of haematological toxicities in CLL studies. The study will include the evaluations of safety and tolerability according to the time points provided in the TIME AND EVENTS SCHEDULE.

Safety assessments will be based on medical review of adverse event reports and the results of vital sign measurements, physical examinations, clinical laboratory tests, ECOG performance status, and other safety evaluations at specified time points as described in the Time and Events Schedules

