# 6.3. Vital Signs and Physical Examination

- Descriptive statistics of temperature, pulse/heart rate, respiratory rate, mean arterial pressure
  and blood pressure (systolic and diastolic values) and changes from baseline will be
  summarized at each scheduled time point
- The percentage of subjects with values beyond clinically important limits will be summarized.
- Listing of vital sign measurements and the change from baseline will be presented for all participants.
- A listing of abnormal vital signs will be presented, including unscheduled visits.

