**Table 4: Normal Ranges for Vital Signs** 

Parameter	Range	Unit
Body temperature	36.1 – 37.2	С
Pulse rate	60 – 100	beats/min
Systolic Blood Pressure	90 – 120	mmHg
Diastolic Blood Pressure	60 – 80	mmHg
Mean Arterial Pressure	70 - 100	mmHg
Respiratory Rate	12 – 20	breaths/min

Physical examination findings will be listed.

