#### 6.4. ECOG Performance Status

Subjects will be listed with its performance status at all the schedule timepoints. Counts and percentages of ECOG will be presented at scheduled visits.

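### Protocol 11.4 promises physical examination summaries that the SAP reduces to a listing; as separate SAP weaknesses, on-study weight has no summary and ECOG is never paired with baseline

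*Protocol*

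**What the plan says.** **Physical examination.** The Physical Examination paragraph of protocol 11.4 specifies three kinds of output: "Physical examination findings will be summarized at each scheduled time point"; "Descriptive statistics of changes from baseline will be summarized at each scheduled time point", together with descriptive statistics at baseline; and "Frequency tabulations of the abnormalities will be made". In SAP 6.3, the only sentence on physical examination stands after Table 4: "Physical examination findings will be listed".

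**Weight.** Protocol 9.2 says "Physical examination and vital sign parameters will include blood pressure, pulse rate, respiratory rate, body temperature, and weight". The Vital Signs paragraph of protocol 11.4 then names temperature, pulse, respiratory rate and blood pressure for analysis, but not weight. SAP 6.3 starts from the same set, "Descriptive statistics of temperature, pulse/heart rate, respiratory rate, mean arterial pressure", and continues with systolic and diastolic pressure. Weight is in neither that list nor Table 4. It is summarised only in SAP Table 1, as a demographic variable. SAP section 2 puts all study data into listings, so on-study weight is listed.

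**ECOG.** Protocol 9.2 bases safety assessment on several sources, including "clinical laboratory tests, ECOG performance status, and other safety evaluations". Protocol 11.4 has no ECOG paragraph. SAP Table 2 summarises ECOG at baseline. SAP 6.4 adds a subject-level listing and says "Counts and percentages of ECOG will be presented at scheduled visits". No shift, change or worst-value table is planned.

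**The concern.** Safety under routine use is the primary objective. The SAP explains in section 6.2 why laboratory data have no conventional baseline. Physical examination, weight and ECOG are different: the Time and Events Schedule marks that row at screening as well as on treatment. Where those values were recorded, a comparison with the pre-treatment state is available, and the SAP does not make it.

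A listing gives no numerator, denominator or percentage, so the study report would not contain the physical examination results that the protocol describes. For ECOG, each visit's percentages describe whoever was assessed at that visit. Two different histories can produce the same table: nobody changed, or equal numbers improved and worsened. If subjects in poorer condition leave earlier, the intermediate-visit percentages drift towards better status although nobody has improved.

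**Working it through.** **1. Text comparison (no assumption needed).**

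| Item | Protocol | SAP |
|---|---|---|
| Physical examination by visit | Promised in 11.4 | Listing only |
| Physical examination, change from baseline | Promised in 11.4 | Absent |
| Frequency of abnormal findings | Promised in 11.4 | Absent |
| Weight on study | Parameter in 9.2; not in the 11.4 vital signs list | Listed; summarised only as a demographic |
| ECOG on study | Safety assessment in 9.2; no analysis in 11.4 | By-visit counts and listing; baseline in Table 2; no pairing |

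The first three rows are a protocol-SAP conflict. The last two are not. For weight there is an argument in between: of the five parameters in protocol 9.2, the 11.4 Vital Signs paragraph covers four, and weight is the continuous measure left to which the change-from-baseline statistics under Physical Examination could apply. That is a reading, not an explicit promise.

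**2. Is there a figure to reproduce?** No. The sample size of 75 follows a committee recommendation, with no formula or precision target. The rest is illustration on assumed data.

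**3. Offsetting shifts.** Assume baseline ECOG 0/1/2 counts of 30/35/10 (N = 75). Let k subjects move from 0 to 1 and k from 1 to 0. The new counts are (30 − k + k) / (35 − k + k) / 10 = 30/35/10 for any k. A paired table would show k/75 worsened (exact 95% CI):

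- k = 5: 6.7% (2.2 to 14.9)
- k = 10: 13.3% (6.6 to 23.2)
- k = 15: 20.0% (11.6 to 30.8)

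**4. Dropout at an intermediate visit, nobody changing.** Protocol 1.2 gives 39% ECOG 0 and 61% ECOG 1 or 2 for the 61 relapsed or refractory subjects of an earlier CLL/SLL study. Applied to 75 subjects that is 29 and 46, so the starting ECOG 0 share is 29/75 = 38.7%. The departure rates are assumptions:

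- 10% of ECOG 0 and 30% of ECOG 1–2 gone: 29 × 0.9 / (29 × 0.9 + 46 × 0.7) = 26.1/58.3 = 44.8%, up 6.1 points
- 10% and 50% gone: 26.1 / (26.1 + 46 × 0.5) = 26.1/49.1 = 53.2%, up 14.5 points

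**5. What the last value recovers.** Return to the 30/35/10 baseline, where ECOG 2 or worse is 10/75 = 13.3%. In an extreme case, 9, 15 or 22 subjects (about 11.8%, 20% and 30% of 75) worsen to ECOG 2 and leave. Among those remaining, ECOG 2 or worse is 10/66 = 15.2%, 10/60 = 16.7% or 10/53 = 18.9%. Counting each subject's last or end-of-treatment value gives 19/75 = 25.3%, 25/75 = 33.3% or 32/75 = 42.7%. The 11.8% is the pooled rate of discontinuation due to adverse events in protocol 1.2, borrowed only as a scale; the other two rates are assumed.

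Steps 3 to 5 show that the mechanism is arithmetically possible. They do not show that it will occur.

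**The case against.** The strongest reply is that worsening has other routes into the report. Protocol 9.2 sends clinically relevant changes to the adverse event section of the CRF, the adverse event definition covers conditions aggravated from baseline, and treatment-emergent events are the primary endpoint. Subjects who stop early have an end-of-treatment assessment, recorded on that CRF page (protocol section 5), so their last ECOG can enter the end-of-treatment column. Listings keep every value. The study is descriptive and single-arm, and the synopsis names only adverse events and laboratory tests as the safety variables to be analysed.

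Most of this stands and limits the point. It does not remove it. Adverse event recording depends on the investigator judging a change clinically relevant, and SAP 6.1 counts events only through the day of last dose, while the discontinuation visit may be the first routine visit after a subject stopped. The end-of-treatment column helps only if early and Month 12 assessments are tabulated together, which SAP 6.4 does not say, and its counts would still be unpaired. None of these routes supplies the summaries promised in protocol 11.4.

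A reader might also infer more than the documents support:

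- That ECOG is reported without baseline. It is not: Table 2 gives it. Only the within-subject comparison is missing.
- That weight and ECOG breach 11.4 as physical examination does. The protocol's own vital signs list omits weight, and 11.4 has no ECOG analysis.
- That the SAP's amendment history should have justified the listing. It logs changes between SAP versions, not departures from the protocol.
- That all three measures certainly have a pre-dose value. Schedule footnote d is permissive, the synopsis records physical examination if performed at a routine visit, and the Day 1 procedures in protocol section 5 name neither weight nor ECOG. Completeness has to be checked.

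**Conclusion.** The physical examination conflict between protocol 11.4 and SAP 6.3 is established from the text alone. The weight and ECOG points hold as weaknesses of the SAP.

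It would be too strong to say that worsening on ibrutinib is masked. It can be obscured in the summary tables, by offsetting shifts at any visit and by dropout at intermediate visits, while listings, adverse event recording and the end-of-treatment assessment give partial protection. The shift of about 6 to 15 points in the ECOG 0 share measures assumed departure rates applied to another study's ECOG mix. It is not an estimate for this trial, which also enrols MCL and CLL with 17p deletion. The 20.0% in the offsetting example likewise rests on an assumed baseline.

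The primary endpoint analysis is unaffected. What is at stake is one protocol-specified safety analysis that would not be delivered and two safety measures left without a paired result. That is enough to justify an inexpensive change.

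**What to change.** In SAP 6.3:

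- Restore the physical examination tabulation as the number and percentage of subjects with a new or worsened abnormal finding since baseline. If the sponsor decides to keep only the listing, the departure from protocol 11.4 should at least be documented.
- Add weight, as observed value and change from baseline, to the summaries at each scheduled time point.

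In SAP 6.4:

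- Add a shift table from baseline ECOG to worst and to last or end-of-treatment ECOG. Use the safety analysis set, restricted to subjects with a baseline value, and report the number available.
- State whether unscheduled assessments count towards the worst value, since the schedule also marks this row at unscheduled visits.

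Keep all listings and the by-visit ECOG counts. Any dropout figures used to motivate the change should be labelled as illustrations on assumed rates.

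The cost is SAP wording and about three descriptive tables. Protocol 17.4 has weight and physical examination details entered directly in the CRF, and ECOG is already planned for listing, so no new data are needed. The downside is minor programming; if baseline values prove incomplete, the paired tables will rest on fewer subjects, which the reported numbers will show.

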## 12. ADVERSE EVENT REPORTING

Timely, accurate, and complete reporting and analysis of safety information from clinical studies are crucial for the protection of subjects, investigators, and the sponsor, and are mandated by regulatory agencies worldwide. The sponsor has established Standard Operating Procedures in conformity with regulatory requirements worldwide to ensure appropriate reporting of safety information; all clinical studies conducted by the sponsor or its affiliates will be conducted in accordance with those procedures.

## Method of Detecting Adverse Events and Serious Adverse Events

Care will be taken not to introduce bias when detecting adverse events or serious adverse events. Open-ended and nonleading verbal questioning of the subject is the preferred method to inquire about adverse event occurrence.

#### Solicited Adverse Events

Solicited adverse events are predefined local and systemic events for which the subject is specifically questioned and which are noted by subjects in their diary.

#### **Unsolicited Adverse Events**

Unsolicited adverse events are all adverse events for which the subject is specifically not questioned in the subject diary.

## 12.1. Definitions

#### 12.1.1. Adverse Event Definitions and Classifications

#### **Adverse Event**

An adverse event is any untoward medical occurrence in a clinical study subject administered a medicinal (investigational or non-investigational) product. An adverse event does not necessarily have a causal relationship with the treatment. An adverse event can therefore be any unfavorable and unintended sign (including an abnormal finding), symptom, or disease temporally associated with the use of a medicinal (investigational or non-investigational) product, whether or not related to that medicinal (investigational or non-investigational) product. (Definition per International Conference on Harmonisation [ICH])

This includes any occurrence that is new in onset or aggravated in severity or frequency from the baseline condition, or abnormal results of diagnostic procedures, including laboratory test abnormalities.

Note: The sponsor collects adverse events starting with the signing of the ICF (refer to Section 12.3.1. All Adverse Events, for time of last adverse event recording).

#### **Serious Adverse Event**

A serious adverse event based on ICH and EU Guidelines on Pharmacovigilance for Medicinal Products for Human Use is any untoward medical occurrence that at any dose:

- Results in death
- Is life-threatening
  (The subject was at risk of death at the time of the event. It does not refer to an event that hypothetically might have caused death if it were more severe.)
- Requires inpatient hospitalization or prolongation of existing hospitalization
- Results in persistent or significant disability/incapacity
- Is a congenital anomaly/birth defect
- Is a suspected transmission of any infectious agent via a medicinal product
- Is Medically Important\*

\*Medical and scientific judgment should be exercised in deciding whether expedited reporting is also appropriate in other situations, such as important medical events that may not be immediately life threatening or result in death or hospitalization but may jeopardize the subject or may require intervention to prevent one of the other outcomes listed in the definition above. These should usually be considered serious.

If a serious and unexpected adverse event occurs for which there is evidence suggesting a causal relationship between the study drug and the event (eg, death from anaphylaxis), the event must be reported as a serious and unexpected suspected adverse reaction even if it is a component of the study endpoint (eg, all-cause mortality).

